1.4.1. PCA Subscale 1: Self-Directed Attitudes Scale Score

1.4.1.1. Self-Directed Attitudes Score at Baseline (T1)

Description: Self-directed Attitudes Scale Score at time point T1 (Baseline) is based on four items (75b, 75c, 75d, and 76a) from the BSL Questionnaire. Responses are scored as 1/Strongly Disagree = 1 point, 2/Disagree = 2 points, 3/Neither Disagree nor Agree = 3 points, 4/Agree = 4 points, and 5/Strongly Agree = 5 points.

Variable: SDA_T1_1

Label: Self-Directed Attitudes Scale Score at T1

Type: Numeric; Range = 1 to 5

Algorithm: SDA_T1_1 = MEAN (BSL75b, BSL75c, BSL 75d, BSL76a)

If all responses are missing, then SDA_T1_1=Missing. Otherwise, calculate the mean of non-missing responses.

1.4.1.2. Self-Directed Attitudes Score at Month 8 Follow-Up (T3)

Description: Self-directed Attitudes Scale Score at time point T3 (Month 8 follow-up) is based on four items (75b, 75c, 75d, and 76a) from the EXQ Questionnaire. Responses are recorded as 1/Strongly Disagree = 1 point, 2/Disagree = 2 points, 3/Neither Disagree nor Agree = 3 points, 4/Agree = 4 points, and 5/Strongly Agree = 5 points.

Variable: SDA_T3_1

Label: Self-Directed Attitudes Scale Score at T3

Type: Numeric; Range = 1 to 5

Algorithm: SDA_T3_1 = MEAN (EXQ75b, EXQ75c, EXQ75d, EXQ76a)

If all responses are missing, then SDA_T3_1=Missing. Otherwise, calculate the mean of non-missing responses.

1.4.1.3. Change in Self-Directed Attitudes Score from Baseline to Month 8 Follow-Up (T1T3)

Description: Difference between Self-Directed Attitudes score at time point T3 (Month 8 follow-up) and time point T1 (Baseline)

Variable: SDA_T1T3_1

Label: Change in Self-Directed Attitudes Score from T1 to T3 (T3-T1)

Type: Numeric; Range = -4 to 4

Algorithm: $SDA_T1T3_1 = SDA_T3_1 - SDA_T1_1$

If SDA score at either time point is missing, then SDA_T1T3_1=Missing.

1.4.2. PCA Subscale 2: Values-Driven Attitudes Scale Score

1.4.2.1. Values-Driven Attitudes (VDA) Score at Baseline (T1)

Description: Values driven Attitudes Scale Score at time point T1 (Baseline) is based on 3 items (76b, 76c, and 76d) from the BSL Questionnaire. Response are scored as 1/Strongly Disagree = 1 point, 2/Disagree = 2 points, 3/Neither Disagree nor Agree = 3 points, 4/Agree = 4 points, and 5/Strongly Agree = 5 points.

Variable: VDA_T1_1

Label: Values-Driven Attitudes Scale Score at T1

Type: Numeric; Range = 1 to 5

Algorithm: $VDA_T1_1 = MEAN (BSL76b, BSL76c, BSL76d)$

If all responses are missing, then VDA_T1_1=Missing. Otherwise, calculate the mean of non-missing responses.

1.4.2.2. Values-Driven Attitudes (VDA) Score at Month 8 Follow-Up (T3)

Description: Values driven Attitudes Scale Score at time point T3 (Month 8 follow-up) is based on 3 items (76b, 76c, and 76d) from the EXQ Questionnaire. Responses are scored as 1/Strongly Disagree = 1 point, 2/Disagree = 2 points, 3/Neither Disagree nor Agree = 3 points, 4/Agree = 4 points, and 5/Strongly Agree = 5 points

Variable: VDA_T3_1

Label: Values-Driven Attitudes Scale Score at T3

Type: Numeric; Range = 1 to 5

Algorithm: $VDA_T3_1 = \text{MEAN}(\text{EXQ76b}, \text{EXQ76c}, \text{EXQ76d})$

If all responses are missing, then $VDA_T3_1 = \text{Missing}$. Otherwise, calculate the mean of non-missing responses.

1.4.2.3. Change in Values-Driven Attitudes (VDA) Score from Baseline to Month 8 Follow-Up (T1T3)

Description: Difference between Values-Driven Attitudes Score at time point T3 (Month 8 follow-up) from time point T1 (Baseline)

Variable: VDA_T1T3_1

Label: Change in Values Driven Attitudes Score from T1 to T3 (T3-T1)

Type: Numeric; Range = -4 to 4

Algorithm: $VDA_T1T3_1 = VDA_T3_1 - VDA_T1_1$

If VDA score at either time point is missing, then $VDA_T1T3_1 = \text{Missing}$.

1.4.3. Scale: Protean Career Attitudes (PCA) Scale

1.4.3.1. Protean Career Attitudes (PCA) Score at Baseline (T1)

Description: The Protean Career Attitudes Score at T1 is obtained by adding the two subscale scores defined above: SDA Score at T1 and VDA Score at T1.

Variable: PCA_T1_1

Label: Protean Career Attitudes Score at T1

Type: Numeric; Range = 1 to 5

Algorithm: $PCA_T1_1 = \text{MEAN}(\text{SDA_T1_1}, \text{VDA_T1_1})$

If either SDA or VDA score is missing, then $PCA_T1_1 = \text{Missing}$.

1.4.3.2. Protean Career Attitudes (PCA) Score at Month 8 Follow-Up (T3)

Description: The Protean Career Attitudes Score at T3 is obtained by adding the two subscale scores defined above: SDA Score at T3 and VDA Score at T3.

Variable: PCA_T3_1

Label: Protean Career Attitudes Score at T3
Type: Numeric; Range = 1 to 5
Algorithm: $PCA_T3_1 = MEAN (SDA_T3_1, VDA_T3_1)$

If either SDA or VDA score is missing, then $PCA_T3_1 = \text{Missing}$.

1.4.3.3. Change in Protean Career Attitudes (PCA) Score from Baseline to Month 8 Follow-Up (T1T3)

Description: Difference between protean career attitudes score at time point T3 (Month 8 follow-up) and time point T1 (Baseline)

Variable: PCA_T1T3_1
Label: Change in Protean Career Attitudes Score from T1 to T3 ($T3 - T1$)
Type: Numeric; Range = -4 to 4
Algorithm: $PCA_T1T3_1 = PCA_T3_1 - PCA_T1_1$.

If PCA score at either time point is missing, then $PCA_T1T3_1 = \text{Missing}$.

2. SECONDARY OUTCOMES

2.1. SELF-REPORTED EMPLOYMENT

The primary employment outcome is based on the change in the number of self-report hours worked per week from T1 to T3.

2.1.1. Change in Self-Reported Hours Worked Per Week from Baseline to Month 8 Follow-Up (T1T3)

Description: Change in hours worked per week from Baseline to Month 8 follow-up (T1 to T3)

Variable: EMPHOUR_T1T3_1

Label: Change in Hours Worked per Week from T1 to T3 (T3-T1)

Type: Numeric; Range = -99 to 99

Algorithm:
If BSL9 = 0 then BSL27 = 0
If EXQ9 = 0 then EXQ27 = 0
EMPHOUR_T1T3_1 = EXQ27 – BSL27

If hours work per week at either time point is missing, then EMPHOUR_T1T3_1=Missing.

2.2. SELF-REPORTED SEXUAL RISK BEHAVIORS

2.2.1. Self-Reported Sexual Risk Behavior at Baseline (T1)

Description: Sexual Risk behavior is measured using items 239 through 244 from the BSL Questionnaire. Responses for each question are either Yes (1), No (0) or Missing (.). Risk Behavior is defined as the mean of responses to the risk behavior questions.

Variable: RISK_T1_1

Label: Self-Reported Sexual Risk Behavior at T1

Type: Numeric; Range = 0 to 1

Algorithm: RISK_T1_1 = MEAN (BSL239, BSL240, BSL241, BSL242, BSL243, BSL244)

If responses for four or more individual risk behavior questions are missing, then RISK_T1_1 = Missing. Otherwise, calculate the mean of non-missing responses.

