#### **8.2.1 Completing the Audio Computer Assisted Self-Interview**

- The participant is reminded of his or her right to discontinue at any time with no penalty and the right to choose to leave any questions unanswered;
- The participant is given headphones and a iPad in an accommodating, private and quiet area;
- The research staff assists with ACASI tutorials; and
- If the participant requires a break, research staff will make sure the computer program is exited and re-entered properly so that the participant's privacy is maintained

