4.2.2. Change in Self-Reported Sexual Risk Behaviors (T1 to T3)

Sexual risk behaviors will be measured using six yes or no (1 or 0) items assessing for engagement in the following behaviors during the 6 months prior to baseline (T1) and 8-month follow-up (T3) assessments:

1. condomless anal intercourse (CAI) with male partner of unknown HIV status
2. anal intercourse with ≥ 3 males
3. sex with male partner with a Sexually Transmitted Infection (STI)
4. CAI with HIV+ male partner
5. anal intercourse with condom failure
6. transactional sex work involvement

Responses will be averaged at each assessment. Change in sexual risk behaviors will be calculated by subtracting the average at baseline from the average at the 8-month follow-up (range: -1 to +1; negative change indicates fewer sexual risk behaviors, while positive change indicates more sexual risk behaviors).

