5.2. Missing Data

Missing responses to survey questions will be ignored and non-missing data will be used to compute the primary and secondary outcomes. If all components for an outcome are missing, then the outcome will be considered missing. For those outcomes with unique missing data rules, the handling of missing data for each individual outcome are described in the appendix. Missing data patterns will be explored prior to the analysis of the primary and secondary outcomes.

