2.2.2. Self-Reported Sexual Risk Behavior at Baseline (T3)

Description: Sexual Risk behavior is measured using items 239 through 244 from the EXQ Questionnaire. Responses for each question are either Yes (1), No (0) or Missing (.). Risk Behavior is as the mean of responses to the risk behavior questions.

Variable: RISK_T3_1

Label: Self-Reported Sexual Risk Behavior at T3

Type: Numeric; Range = 0 to 1

Algorithm: RISK_T3_1 = MEAN (EXQ239, EXQ240, EXQ241, EXQ242, EXQ243, EXQ244)

If responses for four or more individual risk behavior questions are missing, then RISK_T3_1 = Missing. Otherwise, calculate the mean of non-missing responses.

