2.2.3. Change in Self-Reported Risk Behavior from Baseline to Month 8 Follow-Up (T1T3)

Description: Change in Self-Reported Risk Behavior of a participant from Baseline to month 8 follow-up (T1 to T3)

Variable: RISK_T1T3_1

Label: Change in Self-Reported Sexual Risk Behavior from T1 to T3 (T3-T1)

Type: Numeric; Range = -1 to 1

Algorithm: RISK_T1T3_1 = RISK_T3_1 - RISK_T1_1.

If risk behavior at either time point is missing, then RISK_T1T3_1 = Missing.

2.3. CHLAMYDIA INFECTIONS:

Chlamydia will be assessed at T1 (Baseline) and T3 (8-month follow-up) using urine, anal, and oral sample tests.

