2.2.2. Self-Reported Sexual Risk Behavior at Baseline (T3)

Description: Sexual Risk behavior is measured using items 239 through 244 from the EXQ Questionnaire. Responses for each question are either Yes (1), No (0) or Missing (.). Risk Behavior is as the mean of responses to the risk behavior questions.

Variable: RISK_T3_1

Label: Self-Reported Sexual Risk Behavior at T3

Type: Numeric; Range = 0 to 1

Algorithm: RISK_T3_1 = MEAN (EXQ239, EXQ240, EXQ241, EXQ242, EXQ243, EXQ244)

If responses for four or more individual risk behavior questions are missing, then RISK_T3_1 = Missing. Otherwise, calculate the mean of non-missing responses.

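### The sexual-risk change score can rest on different items at T1 and T3, so unchanged behaviour can score as change; the test is biased if item- or answer-related skipping shifts between visits.

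*SAP*

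**What the plan says.** SAP section 4.2.2 (Phase 2) defines the outcome: "Sexual risk behaviors will be measured using six yes or no (1 or 0) items assessing for engagement". The six behaviours are distinct, for example condomless intercourse with a partner of unknown HIV status, condom failure, and transactional sex.

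Appendix 2.2.1 scores T1: "If responses for four or more individual risk behavior questions are missing, then RISK_T1_1 = Missing. Otherwise, calculate the mean of non-missing responses". Appendix 2.2.2 applies the same rule separately at T3: "If responses for four or more individual risk behavior questions are missing, then RISK_T3_1 = Missing. Otherwise, calculate the mean of non-missing responses". Appendix 2.2.3 then sets "RISK_T1T3_1 = RISK_T3_1 - RISK_T1_1", with one condition: "If risk behavior at either time point is missing, then RISK_T1T3_1 = Missing". The Phase 3 SAP repeats all three steps.

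SAP section 5.2 (Phase 2) gives the general rule: "Missing responses to survey questions will be ignored and non-missing data will be used to compute the primary and secondary outcomes". Both SAPs add that missing-data patterns will be explored before the outcomes are analysed. Protocol section 8.2.1 reminds participants of "the right to choose to leave any questions unanswered". SAP section 5.1 tests the change with a paired t-test, or a Wilcoxon signed rank test if normality fails, at an alpha of 0.1.

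**The concern.** A mean of answered items is comparable between visits only if the same items enter both means, or if the items are interchangeable. Six different sexual behaviours are unlikely to be equally common. The minimum of three answered items does not help, because three items at T1 and the other three at T3 still pass.

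The visits also differ in character: one is a first contact, the other an exit visit months after the workshops. If participants withhold particular items, or 'yes' answers, more at one visit than the other, the score moves although behaviour has not. More concealment of 'yes' at T3 would look like a benefit of the intervention; more at T1 would look like harm. There is no comparison group to cancel such an artefact. Reduced HIV risk behaviour is a stated hypothesis, and SAP section 5.1 names sexual risk behaviour in its description of preliminary efficacy.

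**Working it through.** **Inputs from the documents.** Six binary items; at least three answered per visit; change = T3 mean minus T1 mean; alpha 0.1 (taken as two-sided, since sidedness is not stated); at least 50 completers expected in Phase 2 (SAP section 2.3). The documents give no skipping rate, item prevalence or false-positive rate for this score.

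**One participant, behaviour fixed.**
- T1 answers Y,Y,N,N,N,N give 2/6 = 0.33. At T3 the same behaviour with three N items skipped gives 2/3 = 0.67. Change = +0.33.
- With three 'yes' and three 'no' behaviours, answering only the 'yes' items at T1 and only the 'no' items at T3 gives 0/3 - 3/3 = -1, the full range.

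**Assumptions for the group calculation.** n = 50; item prevalences 0.45, 0.30, 0.15, 0.10, 0.15, 0.25 (mean 1.40/6 = 0.233); each T3 item equals its T1 value with probability 0.6 or 0.8 and is otherwise redrawn, so individuals vary but no mean changes.

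**Why a rate difference alone does no harm.** If every answer is skipped with probability 0.15 at T1, the expected share of 'yes' among answered items is 0.233 x 0.85 / 0.85 = 0.233, the same as with any other rate at T3. The expected change is zero.

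**Why an answer-related shift does.** If 'yes' is skipped 15% at T1 and everything else 5%, the T1 share is approximately

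0.2333 x 0.85 / (0.2333 x 0.85 + 0.7667 x 0.95) = 0.1983 / 0.9267 = 0.214.

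At T3 it is 0.233, so the spurious mean change is about +0.019. With persistence 0.8 the simulated SD of the change score is 0.129, so the standard error is 0.129/√50 = 0.0182 and the shift is 1.06 standard errors. Rejection is P(Z > 1.645 - 1.06) + P(Z < -1.645 - 1.06) = about 0.28.

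**Simulation of both scoring rules** (two values = persistence 0.6, 0.8; Monte Carlo error up to about one percentage point):

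| Skipping pattern | SAP rule | Items answered at both visits |
|---|---|---|
| None | 10%, 10% | 10%, 10% |
| All items alike, 20% at T1, 5% at T3 | 10%, 10% | 10%, 10% |
| 'Yes' 15%, other 5%, same at both visits | 10%, 10% | 10%, 10% |
| 'Yes' 15% at T1, 5% otherwise | 21%, 28% | 11%, 11% |
| 'No' 15% at T1, 5% otherwise | 22%, 29% | 12%, 11% |
| Two commonest items 30% at T1, 5% otherwise | 17%, 21% | 10%, 10% |
| 'Yes' 30% at T1, 5% otherwise (strong) | 66%, 81% | 21%, 15% |

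A second set of assumptions (prevalences 0.40, 0.35, 0.15, 0.10, 0.20, 0.15, with correlated items) gives the same picture. The rate is 0.099 when all items are skipped alike at 5% versus 20%. It is 0.119, 0.236 and 0.462 when 'yes' is skipped 10%, 20% and 30% at T3 (5% otherwise). In the last case common-item scoring lowers it only to 0.288.

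**Participants lost.** With random skipping s at each visit, an item is answered twice with probability (1-s)².
- s = 0.10: P(Binomial(6, 0.81) < 3) = 0.014, or 0.7 of 50. The SAP rule loses 1 - (1 - 0.0013)² = 0.003, or 0.1 of 50. Extra loss about 0.6.
- s = 0.20: P(Binomial(6, 0.64) < 3) = 0.129, or 6.4 of 50. The SAP rule loses 1 - (1 - 0.017)² = 0.034, or 1.7 of 50. Extra loss about 5.

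**The case against.** The strongest reply is that most skipping does no harm to the test. Under the first set of assumptions, 10% random skipping gives about half of participants with frozen behaviour a non-zero change. That is mean-zero noise, and the paired test allows for it. This stands: the share of non-zero scores shows that the score is unreliable within a person, not that the test is biased.

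A reader might infer that the false-positive rate doubles or triples whenever skipping differs between visits. The documents do not support that. A difference in rate alone leaves the test at about 10%, and two to three times nominal is one band of an assumption-driven range. The documents establish a right to skip, not a pattern of skipping.

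It can also be said that missing data are already addressed. SAP section 5.2 promises to explore patterns but attaches no action. Protocol section 10.4 provides for multiple imputation where complete-case analysis would lose many participants or bias results, but neither SAP carries this over, and a participant with three answered items counts as complete. Neither provision alters the formula.

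Finally, matching on common items is not a full cure: it removes the item-mix error but leaves part of the bias from hidden 'yes' answers. That also stands.

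**Conclusion.** The scoring rule is defective as written: it subtracts means that may rest on different behaviours. The resulting test is biased only if skipping depends on the item or the answer and that dependence changes between visits. The size cannot be determined from the documents. The figures of about 16% to 29% against a nominal 10% rest on assumed prevalences, persistence and mild skipping patterns at n = 50; stronger patterns give far more, and patterns that do not shift give no inflation.

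The weight is moderate. This is one of several secondary outcomes in an unpowered, exploratory single-arm pilot. A reader might extend the point to the job-seeking self-efficacy and career-attitude change scores, which also average the answered items. Those are graded scales of related items rather than six distinct yes/no behaviours, and no calculation here covers them, so the extension is not made.

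**What to change.** In Appendix 2.2.3 of both SAPs, define RISK_T1T3_1 as the mean of (T3 item minus T1 item) over the items answered at both visits, and set it to missing if fewer than three items are common. Keep the visit-level means from 2.2.1 and 2.2.2 for description, or use their difference as a sensitivity analysis. Report, for each of the six items, the number unanswered at T1 and at T3, so that a shift in skipping can be seen.

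The cost is a few lines of code and the participants counted above. Under random skipping the matched score was at least as precise as the present one despite those losses. The report should say that selective concealment of 'yes' answers can still bias the result.

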2.2.2. Self-Reported Sexual Risk Behavior at Baseline (T3)

Description: Sexual Risk behavior is measured using items 239 through 244 from the EXQ Questionnaire. Responses for each question are either Yes (1), No (0) or Missing (.). Risk Behavior is as the mean of responses to the risk behavior questions.

Variable: RISK_T3_1

Label: Self-Reported Sexual Risk Behavior at T3

Type: Numeric; Range = 0 to 1

Algorithm: RISK_T3_1 = MEAN (EXQ239, EXQ240, EXQ241, EXQ242, EXQ243, EXQ244)

If responses for four or more individual risk behavior questions are missing, then RISK_T3_1 = Missing. Otherwise, calculate the mean of non-missing responses.

2.2.3. Change in Self-Reported Risk Behavior from Baseline to Month 8 Follow-Up (T1T3)

Description: Change in Self-Reported Risk Behavior of a participant from Baseline to month 8 follow-up (T1 to T3)

Variable: RISK_T1T3_1

Label: Change in Self-Reported Sexual Risk Behavior from T1 to T3 (T3-T1)

Type: Numeric; Range = -1 to 1

Algorithm: RISK_T1T3_1 = RISK_T3_1 - RISK_T1_1.

If risk behavior at either time point is missing, then RISK_T1T3_1 = Missing.

2.3. CHLAMYDIA INFECTIONS:

Chlamydia will be assessed at T1 (Baseline) and T3 (8-month follow-up) using urine, anal, and oral sample tests.

2.3.1. Chlamydia Result at Baseline (T1)

2.3.1.1. Chlamydia Result based on Oral Sample at T1

Description: The oral sample collection status is recorded in item 10a of the Biospecimen Collection (BIC1) form and the oral swab Chlamydia result is recorded in item 1a of the Biospecimen Results (BLR1) Form for Baseline (T1).

Variable: CH_ORAL_T1_1

Label: Assessment of Chlamydia using an Oral Test at T1

Type: Numeric; Format: 1=Positive, 0=Negative, .U=Unknown, .N=Not Collected, .R=Refused, .=Missing

Algorithm:

```
If [BIC1] BIC10a = 1 then CH_ORAL_T1_1 = [BLR1] BLR1a
Else if [BIC1] BIC10a=1 and [BLR1] BLR1a=. then CH_ORAL_T1_1 = .U
Else if [BIC1] BIC10a=0 then CH_ORAL_T1_1 = .N
Else if [BIC1] BIC10a=9 then CH_ORAL_T1_1 = .R
Else if [BIC1] BIC10a=. then CH_ORAL_T1_1 = .
```

2.3.1.2. Chlamydia Result based on Anal Sample at T1

Description: The anal sample collection status is recorded in item 11a of the BIC1 form and the anal swab Chlamydia result is recorded in item 2a of the BLR1 Form for Baseline (T1).

Variable: CH_ANAL_T1_1

Label: Assessment of Chlamydia using an Anal Test at T1

Type: Numeric; Format: 1=Positive, 0=Negative, .U=Unknown, .N=Not Collected, .R=Refused, .=Missing

Algorithm:

```
If [BIC1] BIC11a = 1 then CH_ANAL_T1_1 = [BLR1] BLR2a
Else if [BIC1] BIC11a=1 and [BLR1] BLR2a=. then CH_ANAL_T1_1 = .U
Else if [BIC1] BIC11a=0 then ANAL_CH_T1_1 = .N
Else if [BIC1] BIC11a=9 then ANAL_CH_T1_1 = .R
Else if [BIC1] BIC11a=. then ANAL_CH_T1_1 = .
```

2.3.1.3. Chlamydia Result based on Urine Sample at T1

Description: The urine sample collection status is recorded in item 12a of BIC1 form and the urine Chlamydia result is recorded in item 3a of BLR1 Form for Baseline (T1).

Variable: CH_URINE_T1_1

Label: Assessment of Chlamydia using a Urine Test at T1

Type: Numeric; Format: 1=Positive, 0=Negative, .U=Unknown, .N=Not Collected, .R=Refused, .=Missing

Algorithm:

```
If [BIC1] BIC12a = 1 then CH_URINE_T1_1 = [BLR1] BLR3a
Else if [BIC1] BIC12a=1 and [BLR1] BLR3a=. then CH_URINE_T1_1 = .U
Else if [BIC1] BIC12a=0 then CH_URINE_T1_1 = .N
```

Else if [BIC1] BIC12a=9 then CH_URINE_T1_1 = .R
Else if [BIC1] BIC12a=. then CH_URINE_T1_1 = .

2.3.2. Chlamydia Result at Month 8 Follow-Up (T3)

2.3.2.1. Chlamydia Result based on Oral Sample at T3

Description: The oral sample collection status is recorded in item 10a of the Biospecimen Collection (BIC2) form and the oral swab Chlamydia result is recorded in item 1a of the Biospecimen Results (BLR2) Form for 8-Month Follow-up (T3).

Variable: CH_ORAL_T3_1

Label: Assessment of Chlamydia using an Oral Test T3

Type: Numeric; Format: 1=Positive, 0=Negative, .U=Unknown, .N=Not Collected, .R=Refused, .=Missing

Algorithm:
If [BIC2] BIC10a = 1 then CH_ORAL_T3_1 = [BLR2] BLR1a
Else if [BIC2] BIC10a=1 and [BLR2] BLR1a=. then CH_ORAL_T3_1 = .U
Else if [BIC2] BIC10a=0 then CH_ORAL_T3_1 = .N
Else if [BIC2] BIC10a=9 then CH_ORAL_T3_1 = .R
Else if [BIC2] BIC10a=. then CH_ORAL_T3_1 = .

2.3.2.2. Chlamydia Result based on Anal Sample at T3

Description: The anal sample collection status is recorded in item 11a of the BIC2 form and the anal swab Chlamydia result is recorded in item 2a of the BLR2 Form for the Month 8 follow-up (T3).

Variable: CH_ANAL_T3_1

Label: Assessment of Chlamydia using an Anal Test T3

Type: Numeric; Format: 1=Positive, 0=Negative, .U=Unknown, .N=Not Collected, .R=Refused, .=Missing

Algorithm:
If [BIC2] BIC11a = 1 then CH_ANAL_T3_1 = [BLR2] BLR2a
Else if [BIC2] BIC11a=1 and [BLR2] BLR2a=. then CH_ANAL_T3_1 = .U
Else if [BIC2] BIC11a=0 then CH_ANAL_T3_1 = .N
Else if [BIC2] BIC11a=9 then CH_ANAL_T3_1 = .R
Else if [BIC2] BIC11a=. then CH_ANAL_T3_1 = .

